11.3. Adverse Event Categorization

TABLE 3. ISO 14155:2011- ANNEX F - ADVERSE EVENT CATEGORIZATION

Adverse Event	Non-Device Related	Device or Procedure Related
Non-Serious	Adverse Event (AE)	Adverse Device Effect (ADE)
Serious	Serious Adverse Event (SAE)	Serious Adverse Device Effect (SADE)
		
 Anticipated Serious Adverse Device Effect (ASADE)

CONFIDENTIAL AND PROPRIETARY DATA: This document and the information contained herein may not be reproduced, used, or disclosed without written permission from Edwards Lifesciences SA

		
• Unanticipated Serious Adverse Device Effect (USADE)
--	--	---

11.4. Adverse Event Definitions

11.4.1. ADVERSE EVENT DEFINITION (AE)

An adverse event (AE) is defined in ISO 14155:2011 as any untoward medical occurrence, unintended disease or injury, or untoward clinical signs (including abnormal laboratory findings) in subjects, users or other persons, whether or not related to the investigational device.

11.4.2. ADVERSE DEVICE EFFECT (ADE)

An adverse device effect is defined in ISO 14155:2011 as any adverse event related to the use of an investigational medical device. This definition includes:

- Adverse event resulting from insufficient or inadequate instructions for use, deployment, implantation, installation, or operation, or any malfunction of the investigational medical device
- Any event resulting from use error or from intentional misuse of the investigational medical device.

11.4.3. SERIOUS ADVERSE EVENT (SAE)

A serious adverse event (SAE) is defined an adverse event that:

- Led to death
- Led to a fetal distress, fetal death or a congenital abnormality or birth defect
- Led to a serious deterioration in the health of the subject, that either resulted in:
 - a life-threatening illness or injury, or
 - a permanent impairment of a body structure or a body function, or
 - in-patient hospitalization or prolonged hospitalization of existing hospitalization, or
 - medical or surgical intervention to prevent life-threatening illness or injury or permanent impairment to body structure or a body function

NOTE: Planned hospitalizations and procedures scheduled before the patient is enrolled in the registry for a pre-existing condition without serious deterioration in health should not be reported.

11.4.4. SERIOUS ADVERSE DEVICE EFFECT (SADE)

A serious adverse device effect is defined as an adverse device effect that results in any of the consequences characteristic of a serious adverse event or that might have led to any of these consequences if suitable action had not been taken or intervention had not been made or if circumstances had been less opportune.

11.4.5. ANTICIPATED AND UNANTICIPATED SERIOUS ADVERSE DEVICE EFFECTS (ASADE/USADE)

Anticipated adverse events are device- or procedure-related complications that are expected to occur in subjects undergoing aortic valve replacement and concomitant procedures, and that have been identified as potential risks in this investigational

plan, the risk analysis report or in product labeling (Section 4.1: Risks) If these events are deemed to be serious, they should be reported as Anticipated Serious Adverse Device Effects.

Unanticipated adverse device effect (USADE) is defined in ISO 14155:2011 as any serious adverse effect which by its nature, incidence, severity or outcome has not been identified in the risk analysis report.

11.4.6. DEVICE DEFICIENCY AND MALFUNCTION

Device deficiency is defined in ISO 14155:2011 as an inadequacy of a medical device with respect to its identity, quality, durability, reliability, safety or performance. Device deficiencies include malfunctions, use errors and inadequate labeling. Device malfunction is defined in ISO 14155:2011 as a failure of an investigational device to perform in accordance with its intended purpose when used in accordance with the Instructions For Use (Appendix I)

12. Statistical Analysis

This trial is a multi-center, active and non-randomized registry, with maximum planned enrollment up to 300 patients to receive the EDWARDS INTUITY Elite Valve System through a minimally invasive incision. The following sections detail the statistical analysis for this registry.

12.1. ANALYSIS COHORTS

There will be two analysis cohorts for this registry: the enrolled and the per protocol cohort. The following two sub-sections contain the definition for these two cohorts.

12.1.1. ENROLLED COHORT

A subject will be considered enrolled into the registry when he/she has signed the informed consent, met all the registry eligibility criteria.

12.1.2. PER PROTOCOL COHORT

The per protocol cohort will consist of all enrolled patients that leave the operating room with the registry valve in place and had an AVR MIS surgery procedure. All summaries of the safety endpoints and other safety data will be based on the per protocol cohort. The summaries of the primary, secondary and patient related endpoints will also be based on the per protocol cohort.

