In the operating room, the intra-operative exclusion criteria will be assessed by careful examination of the valve anatomy, valve condition and associated structures. Any other intra-operative exclusion criteria or eligibility exclusion criteria may be assessed throughout the procedure.

Adverse events for enrolled patients are collected from the time the subject is in the operating room.

Enrolled patients, due to an intra-op Exclusion criteria can be excluded (defined as intra-op screen failure). The reason for ineligibility will be explained to them and will be documented into the eCRF. Subjects will then be followed by their primary health care provider per best medical practice.

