9.6.1. OPERATIVE DATA COLLECTION REQUIREMENTS

The sponsor will provide a worksheet to note the various activities throughout the procedure. These data will be transferred to the procedure CRF.

- Intra-operative eligibility criteria (Aortic valve anatomy, Aortic valve condition (annulus/leaflets), condition of surrounding structures)
- Procedure Date
- Procedure Time: Cross Clamp Time (XCT), Cardiopulmonary Bypass Time(CPB)
- Surgical Approach (partial hemi-sternotomy or right anterior thoracotomy) and whether conversion to full sternotomy was required
- Implant Data: Valve Model, Serial Number and Valve Size
- Delivery System: Model, Serial Number and Size
- Suture Technique
- Implant Attempts
- Technical Success
- Final Device Implanted
- Implant Evaluation
- Intraoperative Adverse Events/ Complications
- Ventilation time

The subjects for which an EDWARDS INTUTY Elite Valve is attempted, but not successfully implanted or the minimally invasive surgical approach is converted to a full sternotomy after the valve implant procedure is initiated will be followed for 30 days post valve implant procedure. The discharge visit, 30 days FU Phone visit and adverse events if applicable will be collected. The subject will be exited from the registry at after the 30 days FU Phone visit or not until all adverse events associated with the above scenarios' are resolved. Once subjects have completed safety follow-up, they should be exited from the registry.

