11.1. General Reporting Requirements

The EDWARDS INTIITY Elite is CE marked; therefore all adverse events should be recorded in accordance with Medical Device Directive 93/42/EEC, MEDDEV 2.12-1 Guidelines on a Medical Devices Vigilance System, ISO 14155:2011(E), and any other regulations as applicable, and as summarized in Table 2.

Adverse event reporting is an investigator's responsibility and decision. Adverse Events (AE) will be identified and captured on the AE CRF throughout the duration of the registry as they occur and will be followed until they are adequately resolved or explained.

In MISSION Registry, all Serious Adverse Events and Device/Procedure Related Events should be reported as soon as possible but no later than within 72 hours (3 calendar days) after the Investigational center first learns of the event.

All Device-Related Deaths and all Unanticipated Adverse Events (not listed in the risk section of the protocol or IFU) or Serious Device-Related Adverse Events should be reported within 24 hours after the investigational center first learns of the event.

Relevant source documents will be provided to Sponsor for evaluation and endpoints adjudication within 15 working days after the Investigational center first learns of the event. That includes source documents records from outside admissions (hospitalizations out of the enrolling site), which are related to reported adverse events/complications.

Notification to the Sponsor should be done via electronic data system by entering an adverse event into the database or if that's impossible an initial notification can be done by fax or email to the assigned Safety personnel

[contact]

In addition, investigational centers are responsible for reporting serious adverse events to their local Regulatory Bodies in accordance with the applicable requirements.

11.2. ADVERSE EVENTS COLLECTED FOR THIS REGISTRY – REGISTRY ENDPOINTS:

All Registry Endpoints and Potential Endpoints will be adjudicated (reviewed) by an independent CEC committee

TABLE 2. SAFETY ENDPOINTS DEFINITIONS

Complication	Definition
All-cause mortality	All cause mortality includes all exspirations of registry subjects as reported from investigational sites/or adjudicated per CEC

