12.3. SAFETY DATA

- All cause mortality
 - Study valve-related mortality
- Thromboembolism (Stroke, TIA, and Non cerebral embolism)
- Valve Thrombosis
- Major Bleeding event

- Endocarditis (study valve)
- Structural valve deterioration
- Non Structural valve deterioration
 - Paravalvular Leak minor
 - Paravalvular Leak major
 - Other non SVD
- Hemolysis
- Reoperation
 - Trial valve reoperation
- Study valve explants
- Implant-related new or worsened cardiac conduction disturbance requiring permanent pacemaker implant
- Renal Failure
- Respiratory Failure
- Deep Sternal Wound infection

Early adverse events within 30 days of procedure will be reported as the number of events divided by the number of enrolled subjects. Linearized rates will be used to summarize adverse events for the late (>30 days) post-operative period. The linearized rates will be calculated as the number of late events divided by the total number of late-subject years.

Percentages for the early events and linearized rates for the late events also will be calculated for all other complications observed in the trial.

Actuarial rates based on the method of Kaplan - Meier will be calculated for each of the safety endpoints at thirty days and six months; the number of subjects at risk for death will be reported at each of these intervals.

On top of Implant-related new or worsened cardiac conduction disturbance requiring permanent pacemaker, the counts and percentage of subjects who experience new or worsening cardiac rhythm or conduction disturbances will be calculated at each follow-up visit. The identification of “new and worsening” cardiac rhythm or conduction disturbance will be based on a comparison to the previous visit.

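### Section 12.1.2 puts every summary on the per-protocol cohort, while 12.2.3, 12.2.5 and 12.3 use enrolled subjects, and the plan does not say which rule prevails

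*Combined protocol and SAP*

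**What the plan says.** Section 12.1 provides two cohorts, enrolled and per protocol. Section 12.1.2 defines the second as "all enrolled patients that leave the operating room with the registry valve in place and had an AVR MIS surgery procedure". It then assigns everything to it: "All summaries of the safety endpoints and other safety data will be based on the per protocol cohort", and "The summaries of the primary, secondary and patient related endpoints will also be based on the per protocol cohort". No exception is given.

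The endpoint sections differ:

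- 12.3: "Early adverse events within 30 days of procedure will be reported as the number of events divided by the number of enrolled subjects".
- 12.2.3 takes technical and procedural success over enrolled patients, and 12.2.5 summarises hospital and ICU stay in the enrolled cohort.
- 12.2.1 names no population for cross-clamp time. First-attempt success, listed in 7.2, has no paragraph in 12.2.

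On data collection, 9.4 says "Adverse events for enrolled patients are collected from the time the subject is in the operating room". Section 9.6.1 covers subjects with a failed implant attempt and those "converted to a full sternotomy after the valve implant procedure is initiated will be followed for 30 days post valve implant procedure", with adverse events collected. Table 2 in 11.2 says "All cause mortality includes all exspirations of registry subjects as reported from investigational sites/or adjudicated per CEC". Of subjects excluded during surgery, 9.4 says "Subjects will then be followed by their primary health care provider per best medical practice".

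Appendix C adds to the per-protocol definition that no intra-operative exclusion criterion is met. Item 6 of 8.4 includes a switch to full sternotomy among those criteria. Section 12.1.2 does not repeat this condition.

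**The concern.** Two analysts who both follow the plan could report different early event rates, because one rule fixes the subjects and another fixes the denominator. If both are obeyed, numerator and denominator come from different cohorts. The subjects left out of the numerator are those whose implant failed, and probably those converted to full sternotomy. The registry follows these subjects for 30 days specifically to collect their events. On a literal reading a death in the operating room is also left out, since that subject never leaves with the valve in place.

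For first-attempt success, the cohort is defined partly by the outcome, because leaving with the valve in place is a condition of entry. Section 2.2 says the results will support publications and marketing information, so the denominators should be settled before the data are seen.

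**Working it through.** **1. The plan's own figure.** Inputs from 12.5: 300 registry patients, 479 published patients, 15-minute difference, published SD 16.0, 5% error rate; two-sided test from 12.2.1. The registry SD is not stated; 16 is assumed. z = 15 / (16 × √(1/479 + 1/300)) = 15 / 1.178 = 12.7, so power is above 99.9%. The stated figure of more than 90% is reproduced, and the choice of cohort does not endanger power.

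**2. The rules side by side.**

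| Endpoint | 12.1.2 | Endpoint section |
|---|---|---|
| Early safety | per protocol | enrolled denominator (12.3) |
| Technical, procedural success | per protocol | enrolled (12.2.3) |
| Hospital and ICU stay | per protocol | enrolled (12.2.5) |
| First-attempt success | per protocol | none |
| Cross-clamp time | per protocol | no population named (12.2.1) |

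**3. Early safety rate.** Every input here is assumed except 300, the planned size. Of 300 enrolled, 10 have no implant attempt and 15 have a failed implant or conversion, which leaves 290 attempted and 275 per protocol. There are 14 events in per-protocol subjects, 1 to 3 in the failed or converted, and none in the rest.

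- 12.1.2 and 12.3 together, literally: 14/300 = 4.7%
- Per protocol throughout: 14/275 = 5.1%
- All events over enrolled: 15/300 to 17/300 = 5.0% to 5.7%
- Attempted implants: 15/290 to 17/290 = 5.2% to 5.9%

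Once there is any event, the literal rate is below the per-protocol rate whenever anyone enrolled is excluded. It is below the all-enrolled rate whenever an excluded subject has an event. One omitted death is 1/300 = 0.33 points.

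A wider set of assumptions takes a 5% rate in per-protocol subjects, 20% to 40% in excluded subjects, and an excluded share f of 2%, 5% or 10%. The literal rate is 5% × (1 − f) = 4.9%, 4.75% or 4.5%. With all events over enrolled, the rate is 5.3–5.7%, 5.75–6.75% or 6.5–8.5%.

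**4. First-attempt success, per 100 attempted (assumed).** Let 5 succeed only at the second attempt and a never receive the valve.

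- a = 1: 94/100 = 94.0%; per protocol 94/99 = 94.9%; difference 0.9 points
- a = 4: 91/100 = 91.0%; per protocol 91/96 = 94.8%; difference 3.8 points

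If 3 first-attempt successes are converted and also leave the cohort:

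- a = 1: 91/96 = 94.8% against 94.0%; difference 0.8 points
- a = 0: 92/97 = 94.8% against 95/100 = 95.0%; the sign reverses

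**5. Cross-clamp time (assumed).** Shift = share removed × extra minutes in the removed operations. It is zero if those operations are no longer than the rest. With 2% removed and 30 extra minutes it is 0.6; with 8% and 60 minutes it is 4.8. A 15-minute per-protocol reduction would then be 14.4 to 10.2 minutes among attempted implants. In the worst corner the SD widens to √(256 + 0.08 × 0.92 × 3600) = 22.8, and t = 10.2 / √(22.8²/300 + 16²/479) = 6.8.

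**The case against.** The best defence is that a specific rule displaces a general one. Sections 12.2.3, 12.2.5 and 12.3 set their own populations, so 12.1.2 would apply only where nothing else is said. Events in failed implants, which 9.4 and 9.6.1 collect, would then be counted over enrolled subjects. This is a reasonable reading, and for technical success and stay the more natural one. But the plan does not state it, and the wording of 12.1.2 is unqualified. It also leaves first-attempt success and the two per-protocol definitions unresolved. Table 2 adds little either way: it defines what counts as a death, not whom to analyse.

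For cross-clamp time the defence is stronger. Section 2.2 restricts the registry to patients receiving the valve, so a per-protocol comparison fits the stated target. An analysis of all attempted implants is therefore a useful supplement and not a correction.

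Section 9.6.1 also partly settles who is followed: its 30-day rule applies to conversions after the implant procedure has begun, which leaves earlier intra-operative exclusions to 9.4. However, 9.9 and Appendix C omit that timing.

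Finally, the spread of early rates in the first example is small (4.7% to 5.9%), and no input rate comes from the documents. Both are true, and the case rests on the conflict in the text.

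**Conclusion.** The conflict stands and should be fixed. The plan gives two populations for early safety, for technical and procedural success, and for stay, with no order of precedence. Obeying 12.1.2 and 12.3 together gives a mismatched rate that omits events the registry collects. First-attempt success falls to the per-protocol cohort by default and loses final implant failures.

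A reader might go further in four ways that the documents do not support:

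- That adverse events of failed implants and conversions are certainly absent from every safety summary. This holds only if 12.1.2 overrides 12.3. For conversions it also rests on an inference from Appendix C with item 6 of 8.4.
- That technical success will be about 100% by construction. That needs the general sentence to override the explicit wording of 12.2.3.
- That first-attempt success must be overstated because only failures are removed. Converted first-attempt successes may leave too. The net error is usually upward, but its size and sign depend on unknown rates.
- That the cross-clamp result is biased in a known direction or at risk. The documents show no direction and do not say how the published comparator handled conversions. At a true 15-minute per-protocol effect, significance survives even the worst corner assumed above.

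The sizes are illustrations only, since no failure, conversion or event rate is given.

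**What to change.** (a) Replace the two blanket sentences in 12.1.2 with one cohort per endpoint:

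- Technical and procedural success, hospital and ICU stay: enrolled, as 12.2.3 and 12.2.5 already say.
- First-attempt success: all subjects in whom a registry-valve implant was attempted.
- Early safety: numerator and denominator from the same cohort, including failed implants, conversions and deaths in the operating room. This can be all enrolled, as 12.3 has it, or all attempted implants. With the latter, list subjects excluded before an attempt separately, with reasons and any adverse events.
- Late rates: subjects still in follow-up after 30 days.

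(b) Use one per-protocol definition in 12.1.2 and Appendix C that says how conversions are classed. Reconcile 9.4 and 9.9 with the timing condition in 9.6.1, and define when the implant procedure counts as begun.

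(c) Keep the per-protocol cross-clamp comparison as primary. Optionally add a supportive analysis of cumulative clamp time in all attempted implants, stating that the comparator's handling of conversions is not in the documents.

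The cost is mainly wording. Clamp time, implant attempts and the occurrence of conversion are already on the 9.6.1 list. That list does not clearly record whether conversion came before or after the implant was begun, so one CRF item may be needed. Some reported rates may be slightly less favourable.

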12.2. PERFORMANCE DATA

12.2.1. CROSS CLAMP TIME

Cross clamp time will be summarized by central tendency and variability estimators such as mean, median, standard deviation and interquartile range.

Cross clamp time collected with EDWARDS INTUITY Elite valves from the registry will be compared to cross clamp time derived from published data in conventional valves using an MIS approach via a two-sided student's t-test.

Merck et al²¹ have published to date the largest European dataset on Cross Clamp Time with conventional valves within the MIS setting and this dataset will be used as a comparator.

Cross Clamp time will be stratified by surgical approach (i.e. Upper Hemi-Sternotomy and Anterior Right Thoracotomy). If necessary, other potential confounding factors will be adjusted for using appropriate statistical modeling techniques.

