12.5. SAMPLE SIZE

The sample size of 300 patients has been calculated to ensure that the test of the primary hypothesis in the registry has sufficient power. For the purposes of a power

calculation, we assume the data follow a t-distribution with a 15 minute reduction in cross-clamp time in the EDWARDS INTUITY ELITE group as compared to the cohort published in Merck et al; if a larger reduction is assumed, the power of the statistical test would of course be higher. The cohort of MIS patients in Merck et al. has a total of 479 patients with a mean cross-clamp time of 59.4 ± 16.0 minutes. Assuming a 5% false positive rate, the test of the primary hypothesis has greater than 90% power.

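### Section 12.2.1 names a Student's t-test for groups of unequal size with no registry SD to support equal variances; specifying Welch's test is a free, minor improvement

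*Combined protocol and SAP*

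**What the plan says.** Section 12.2.1 (Cross Clamp Time) sets the registry's cross clamp time against a value "derived from published data in conventional valves using an MIS approach via a two-sided" Student's t-test. It names no variance assumption, no unequal-variance option and no confidence interval for the comparison.

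Section 12.5 (Sample Size) supplies the comparator: the published cohort "has a total of 479 patients with a mean cross-clamp time of 59.4 ± 16.0 minutes". For the effect, "we assume the data follow a t-distribution with a 15 minute reduction in cross-clamp time". On error and power it says: "Assuming a 5% false positive rate, the test of the primary hypothesis has greater than 90% power". It gives no SD for the registry group.

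On registry size, section 12.5 states that "The sample size of 300 patients has been calculated to ensure that the test of the primary hypothesis in the registry has sufficient power". The synopsis and the opening of section 12 make 300 a ceiling. Section 12.1.2 bases the primary endpoint on the per protocol cohort, and section 12.4 uses available cases only, so the number analysed may be lower.

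**The concern.** The equal-variance t-test pools the two sample variances. When group sizes are equal, pooling does little harm even if the spreads differ. When sizes differ, the pooled standard error is too small if the smaller group has the larger SD, and too large if it has the smaller SD. Here the registry is the smaller group.

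Nothing in the documents supports equal spread, and there are reasons for a difference in either direction. The registry uses a three-suture valve with an expandable frame, recruits at up to 30 centres, allows two surgical approaches, and records clamp time cumulatively within the operation with up to two placement attempts. On the other side, surgeons must meet experience thresholds, and the per protocol cohort leaves out patients who do not leave theatre with the registry valve or did not have a minimally invasive procedure.

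What is at stake is whether the p-value of the primary hypothesis test has the 5% error the plan states.

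**Working it through.** **Inputs.** Comparator n2 = 479, mean 59.4, SD s2 = 16.0 (section 12.5; the ± figure is read as an SD). Registry n1 = 300 (section 12.5, a maximum). Difference 15 minutes, 5% error (section 12.5), two-sided (section 12.2.1). Registry SD s1 is not given; it is assumed and varied from 8 to 32 minutes.

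**Step 1: the plan's power figure.** With a common SD of 16:

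- SE = 16 × √(1/300 + 1/479) = 1.178
- noncentrality = 15 / 1.178 = 12.73 on 777 degrees of freedom
- power is about 1.000

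The stated figure of more than 90% is therefore correct as a lower bound.

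**Step 2: actual error of the equal-variance test.**

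- Pooled variance: sp² = [(n1 − 1)s1² + (n2 − 1)s2²] / (n1 + n2 − 2)
- Pooled SE = sp × √(1/n1 + 1/n2)
- Correct SE = √(s1²/n1 + s2²/n2)
- Actual two-sided error ≈ 2 × [1 − Φ(1.963 × pooled SE / correct SE)], where 1.963 is the t critical value on 777 degrees of freedom

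Example with s1 = 20: sp² = (299 × 400 + 478 × 256) / 777 = 311.4, so sp = 17.65. Pooled SE = 1.299. Correct SE = √(400/300 + 256/479) = 1.367. The ratio is 0.951, 1.963 × 0.951 = 1.866, and the error is 6.2%.

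| Assumed registry SD | Pooled SE | Correct SE | Ratio | Actual error | 95% half-width, pooled | 95% half-width, Welch |
|---|---|---|---|---|---|---|
| 10 | 1.031 | 0.932 | 1.106 | 3.0% | 2.02 | 1.83 |
| 12 | 1.074 | 1.007 | 1.067 | 3.6% | 2.11 | 1.98 |
| 16 | 1.178 | 1.178 | 1.000 | 5.0% | 2.31 | 2.31 |
| 20 | 1.299 | 1.367 | 0.951 | 6.2% | 2.55 | 2.68 |
| 24 | 1.434 | 1.567 | 0.915 | 7.2% | 2.81 | 3.08 |
| 32 | 1.729 | 1.987 | 0.870 | 8.8% | 3.39 | 3.91 |

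With fewer registry patients the departure grows. If 200 were analysed (an assumption), the error would be 2.8% at SD 12, 7.3% at SD 20 and 9.4% at SD 24.

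**Step 3: Welch's test.** Simulation with 300 against 479 and 200,000 runs per setting gives an error of 4.9% to 5.0% at registry SDs of 8, 12, 16, 20, 24 and 32. Simulated error for the equal-variance test agrees with the formula (for example 3.6% at SD 12 and 7.3% at SD 24). Welch power at 15 minutes stays above 99.9% throughout.

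**Step 4: could the conclusion change?** At a 15-minute difference and registry SD 32, z = 15 / 1.987 = 7.5. At SD 24 the two tests disagree only if the observed difference lies between 2.81 and 3.08 minutes.

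**The case against.** The strongest case on the other side is that this is a second-order matter in a non-randomised comparison with a published cohort. Confounding and clustering across up to 30 centres could affect the 5% far more, and Welch's test cures neither. That stands, and it limits the severity.

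The direction is also uncertain. If spread scaled with the mean (an assumption), the planned mean of 59.4 − 15 = 44.4 would imply an SD of 16 × 44.4 / 59.4 = 12. The equal-variance test would then be conservative, at 3.6%. The per protocol restriction and the surgeon experience thresholds might narrow the spread as well. None of this establishes a smaller SD, and many centres could widen it. It is a fair reason not to present the issue as error inflation.

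Some stronger readings are tempting but not supported:

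- A reader might infer that the plan prescribes pooled variances. It does not; that is the usual meaning of the test's name. If the sponsor intended another form, the text leaves it unstated.
- A reader might infer that a planned confidence interval is wrong. Neither section plans an interval for this comparison; the half-widths above show what each method would give.
- A reader might infer that the test is sound only if the registry SD is 16. The condition is equality of the two population SDs; 16.0 is the comparator's sample value.
- A reader might combine a large SD with a severe enrolment shortfall to obtain a much larger error. Enrolment is capped at 300, but the documents give no such shortfall as a scenario.
- A reader might infer that the primary conclusion or the power statement is at risk. Steps 1 and 4 show that neither is at the planned difference.

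**Conclusion.** The point holds as a minor one. The named test ordinarily assumes equal variances, the group sizes are unequal, and no registry SD is available to support the assumption. With 300 analysed and a comparator SD of 16, the stated 5% becomes about 3.6% at registry SD 12, 6.2% at SD 20 and 7.2% at SD 24. Between SD 12 and SD 20 the half-widths of the two methods differ by only about 0.13 minutes.

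These figures rest on assumed registry SDs, on reading the test as the equal-variance form, and on independent patients. The case for acting is that a better-specified method is available from the same inputs, for the comparison that carries the primary hypothesis.

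**What to change.** In section 12.2.1, replace the Student's t-test with a two-sided Welch (unequal-variance) t-test at the 5% level. State that the mean difference in cross clamp time will be reported with its Welch 95% confidence interval, using the published n, mean and SD cited in section 12.5.

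The cost is a short text change and one added reported interval. No extra data or patients are needed. If the SDs are equal, almost nothing is lost: the half-width at SD 16 is 2.3133 against 2.3125 minutes. If the registry SD is larger than the comparator's, the interval is wider than the pooled one, by about 0.26 minutes at SD 24, because the pooled one understates the uncertainty. Confounding and centre clustering need separate treatment.
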